10.3.2 Safety Endpoint Analysis

The incidence rates of adverse events (including those listed under the primary and secondary safety endpoints) will be calculated as the number of events per number of treatments as well as tallied per subject. Adverse event rates will be summarized with 95% exact binomial confidence bounds for both the investigational and control groups.

The adverse events of each group will also all be stratified by their (1) seriousness, (2) severity, (3) relatedness to device, (4) relatedness to procedure, and (5) anticipated status.

Any events with onsets occurring between sessions will be associated with the group representing the device used at the last session.

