1.11 NUMBER OF SUBJECTS

Between 15 and 20 subjects (at least 87 test sessions required)

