1.12 STUDY DURATION

The study will be conducted over a maximum of nine (9) dialysis sessions (first three (3) are controls) for each patient. Typically, a patient will have three sessions in one week so that the study will last three (3) weeks per patient. Each session usually lasts around three hours. Any adverse events that are reported after the study session (e.g., a hematoma in the days following the session) will also be catalogued and reported. Adverse events will be recorded up until the next dialysis treatment or for one week following the last session if no additional sessions are planned.

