1.23 SCHEDULE OF ACTIVITIES (SOA)

Table 1: Schedule of Activities

	Enrollment Visit	Control Dialysis Sessions (Visit 1-3)	Test Dialysis Sessions (Visit 4-9)	Final Study Visit (7-10 days after Visit 9)
Informed Consent	X			
Inclusion/Exclusion	X			
Demographics	X			
Medical History Form	X			
Vital Signs	X			
Adverse Event Form	X	X	X	X
Therapy Assessment Form, including the following: 
• Treatment success/failure• Blood alarms• Flow rates• Prescribed treatment time• Achieved treatment time• Prescribed blood flow rate• Achieved blood flow rate• Ability to cannulate fistula		X	X	
Patient Survey			X	
Clinician Survey		X	X	

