5.2 Scientific Rationale for Study Design

The study is designed to confirm the safety, performance, and usability of the V Needle, a new medical device. The device will be tested by comparing the ability to successfully complete hemodialysis sessions to commercially available devices as determined by a clinician.

Additionally, the rates of adverse events will be compared to rates measured using commercially available devices, providing a comparator with data collected under similar circumstances and in the same patient population.

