9.2.2 AE and Device Deficiency Documentation

All AEs will be monitored for all participants, from the time of signing consent through to the final study visit. All AEs, including SAEs, must be detailed in the source documents and reported in a timely manner to the Sponsor by completing an AE page in the CRF. Each unique event must be documented separately.

AEs can be based upon subject report, questionnaires, medical reports or other medical examinations. AEs should be documented in terms of a medical diagnosis. When this is not possible, the AE should be documented in terms of signs and/or symptoms observed by the Investigator or reported by the subject at each study visit. For each medical diagnosis or sign and/or symptoms the Investigator will provide information on dates (onset/resolution), severity, relationship to the medical device, action(s) taken and outcome.

Any AEs should be followed until the event is resolved (with or without sequelae). If an event is ongoing at the time of study completion or termination, the participant will be followed until resolution or Investigator determination that the subject's condition is stable. Documentation of stabilization must be recorded in the participant's source documents. If the Investigator learns of any SAE at any time after a participant has been discharged from the study, and he/she considers

the event reasonably related to the study device and/or study procedure, the Investigator will record the occurrence in the subject's source documents and promptly notify the Sponsor.

If adverse events occur, the first concern will be the safety of the subject. Appropriate medical intervention will be made as soon as possible. Treatment of any AEs is at the sole discretion of the Investigator and according to current good medical practice. Any medication administered for the treatment of an AE should be recorded in the CRF.

All device deficiencies, including serious incidents (a device deficiency that might have led to a SADE if a) suitable action had not been taken, b) intervention had not been made, c) if circumstances had been less fortunate), shall be documented throughout the study in the source documents and appropriately reported on a device deficiency page of the CRF.

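### AE rates per treatment are clustered counts but get exact binomial bounds, which are too narrow for common AEs; the end of V Needle AE counting after Visit 9 is also inconsistent, so the two needles' windows may not match

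*Combined protocol and SAP*

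**What the plan says.** **Rate and interval.** Section 10.3.2 says that AE incidence "will be calculated as the number of events per number of treatments as well as tallied per subject". It then adds: "Adverse event rates will be summarized with 95% exact binomial confidence bounds for both the investigational and control groups". Section 9.2.2 requires: "Each unique event must be documented separately". Section 10.3.1 pools three control and six V Needle sessions per subject, giving 54 and 108 sessions from 18 subjects. Section 1.11 allows 15 to 20 subjects. Section 10.4.1 presents summaries at session level; its only within-subject exception is the additional analysis of the primary performance measure.

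**Use of the rates.** Section 5.2 says that "the rates of adverse events will be compared to rates measured using commercially available devices"; sections 1.1 and 1.8 say the same in substance. Section 10.3.2 names no test or threshold for this comparison.

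**Attribution and end of counting.** Section 10.3.2: "Any events with onsets occurring between sessions will be associated with the group representing the device used at the last session". For the end of recording:
- Section 1.12 has AEs "recorded up until the next dialysis treatment or for one week following the last session if no additional sessions are planned".
- Sections 1.23, 9.1.4 and 9.2.2 together run collection to a final visit 7 to 10 days after Visit 9.
- Section 9.2.13 ends it 7 days after the last day of participation.

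**Device-related events.** Section 9.2.1 defines adverse device effects (ADEs), and hence serious ones (SADEs), for the investigational device only.

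**The concern.** An exact binomial bound fits a number of yes/no outcomes from independent trials. Events per treatment is a different quantity. One session can produce several events, and the same subject supplies up to six V Needle sessions, so events may concentrate in a few subjects. Both features add variance that the bound ignores. If events in a category outnumber treatments, no binomial bound exists at all.

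The second issue concerns the comparison itself. A control session's events normally stop counting when the next session starts. If the last V Needle session carries a longer tail, the V Needle is charged for days that no control session has, and those days include usual dialysis sessions that are not in its denominator.

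The study is meant to support marketing clearance, and readers will set the two rates and their intervals side by side. For frequent AEs they would see too much precision. Part of any apparent difference between needles could come from which follow-up section the analyst chose.

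**Working it through.** **Inputs from the documents.** 18 subjects; 18 x 6 = 108 V Needle and 18 x 3 = 54 control sessions (section 10.3.1; both products reproduce). Three sessions a week, so a mean gap of 7/3 days (section 1.12). Section 10.3.2 itself states no figure to reproduce.

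**Assumed.** AE rate r per session and between-subject coefficient of variation (CV) of that rate.

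**Step 1: size of the variance error.** With Poisson counts and gamma variation between subjects, over m sessions each, the true variance of the estimated rate divided by the binomial variance is (1 + m r CV²)/(1 - r). For the V Needle (m = 6), next to the simulated coverage of the 95% exact binomial bound:

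| r | CV | variance ratio | SE ratio | coverage |
|---|---|---|---|---|
| 0.02 | 0 | 1/0.98 = 1.02 | 1.01 | 98% |
| 0.02 | 1 | 1.12/0.98 = 1.14 | 1.07 | 97% |
| 0.1 | 0 | 1/0.9 = 1.11 | 1.05 | 96% |
| 0.1 | 1 | 1.6/0.9 = 1.78 | 1.33 | 89% |
| 0.2 | 0 | 1/0.8 = 1.25 | 1.12 | 93% |
| 0.2 | 1 | 2.2/0.8 = 2.75 | 1.66 | 79% |
| 0.4 | 0 | 1/0.6 = 1.67 | 1.29 | 89% |
| 0.4 | 1 | 3.4/0.6 = 5.67 | 2.38 | 62% |

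Coverage is from gamma-Poisson simulation with at least 20,000 runs per cell. At r = 0.2 and CV 1 it is 80% with 15 subjects and 79% with 20. The control group (m = 3) is milder: 91%, 89% and 72% at r = 0.1, 0.2 and 0.4 with CV 1.

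**Step 2: a second model.** With at most one event per session (beta-binomial) and a true rate of 10-30%, V Needle coverage is 93-94% at a within-subject correlation of 0.05, 91-92% at 0.1 and 80-81% at 0.3. Clustering alone is therefore enough to cause the loss.

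**Step 3: rare events.** At r = 0.02, coverage is 96-98% for CV up to 1.41 and 95% at CV 2. With zero events the upper limits are nearly the same. For 108 sessions, binomial 1 - 0.025^(1/108) = 3.36% and Poisson -ln(0.025)/108 = 3.42%; for 54 sessions, 6.60% and 6.83%.

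**Step 4: AE window.** Take identical needles, constant daily risk and no hold.
- Control: (3 x 7/3)/3 = 2.33 days per treatment.
- V Needle, tail to the next dialysis: (5 x 7/3 + 7/3)/6 = 2.33; ratio 1.0.
- V Needle, 7-day tail: (5 x 7/3 + 7)/6 = 3.11; ratio 1.33.
- V Needle, 10-day tail: (5 x 7/3 + 10)/6 = 3.61; ratio 1.55.

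If half the events are tied to the session itself, the last two become (1 + 1.33)/2 = 1.17 and (1 + 1.55)/2 = 1.27.

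**The case against.** **The safety analysis is descriptive and the primary measure is rare.** True. A reader might infer that the SADE bounds are unsound; step 3 shows that they hardly move. Only strong clustering changes this: two-sided coverage is about 91% at a rate of 1-2% with a within-subject correlation of 0.3, and every miss is at the lower limit, which matters least for safety. Sections 9.2.1 and 9.2.7 also keep expected pain, bleeding and minimal bruising out of the AE count, so no category is known to be common.

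**The coverage contrast depends partly on holding CV fixed.** At CV 1.41 the implied within-subject correlation, r CV²/(1 + r CV²), is about 0.04 at r = 0.02 and 0.28 at r = 0.2. So the line between rare and common is less sharp than the table suggests. The direction stands, and the shortfall at 0.2 and above appears with no between-subject variation at all.

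**The per-subject tally shows where events came from.** It does, but no interval is stated for it. Counting treatments with at least one event does not cure the problem either: at r = 0.2 on the V Needle, binomial coverage is 97% with no variation but 88% at CV 1.

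**The windows can be read as matched.** A reader might infer that they are definitely unequal. The documents do not establish that. These are chronic dialysis patients, and if sessions in sections 1.12 and 10.3.2 means any dialysis, both windows end at the next one. Sections 9.1.4, 9.2.2 and 9.2.13 govern collection and do not define an analysis numerator. A tail of 14 to 17 days, from counting section 9.2.13's 7 days after the final contact, is strained: section 1.23 schedules nothing after that contact, and section 9.1.4 makes it the check for further AEs. The direction is not fixed either. The FDA hold in section 5.1 could lengthen the gap between Visits 3 and 4 for patients after the fifth and so add control exposure, within the 40-day limit in section 1.24. What stands is that the plan does not say which end applies.

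**Conclusion.** The interval is wrong as written for events per treatment. For common AEs it overstates precision: coverage is about 93% at 0.2 and 89% at 0.4 events per session with no between-subject variation, and about 79% and 62% at CV 1 (V Needle, 18 subjects). For events as rare as 0.02 per session it is adequate unless clustering is strong. The mismatch between count and binomial bound can be read directly from the text; its practical weight rests on an assumed AE rate and CV.

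The window point is smaller. The sections conflict on the end of V Needle counting, and with the attribution rule a 7-10 day tail would give the V Needle 1.33-1.55 times the control exposure per treatment, assuming constant daily risk and no hold. This is an unspecified cut-off, not a demonstrated mismatch.

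No test or success criterion depends on either part. The effect is on how rates and intervals for common AEs are read. Both should be settled before the data are analysed.

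**What to change.** 1. **Events per session:** replace the binomial bound with a subject-clustered robust Poisson interval (t with number of subjects minus 1 degrees of freedom), and use an exact Poisson interval when a category has fewer than 5 events. With 18 subjects this covers 93-97% for CV 0 to 1.
2. **Subjects with at least one event:** keep the exact binomial bound here only. State that the proportions are not comparable between needles, since the V Needle has six sessions and control three. At an equal, independent risk of 0.05 per session they would be 1 - 0.95^6 = 26% and 1 - 0.95^3 = 14%.
3. **Window:** reconcile sections 1.12, 1.23, 9.1.4, 9.2.2 and 9.2.13. For the descriptive needle comparison, count events in both groups from the start of each study session to the start of the next dialysis with any needle. Continue to collect all later AEs and report them alongside, by last study needle, so that delayed V Needle events stay visible.
4. **Labels:** mark ADE and SADE rates as V Needle only; under the definitions a control value is not an observed rate.

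**Cost:** SAP wording, a table label and minor programming; no new data. Intervals for common AEs widen. At 0.2 per session and CV 1, mean V Needle width goes from 0.156 to at most 0.277, the upper figure being the width if the outer limits of the clustered and exact Poisson intervals are taken. At 0.02 it goes from 0.062 to at most 0.066. Coverage can still fall to about 90% at CV 1.41 and 85% at CV 2. The matched window leaves late events out of the compared rate, and charging them to the V Needle would be the more conservative choice, so the separate report in item 3 is essential.

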1.1 PROTOCOL SUMMARY

In patients undergoing hemodialysis for the treatment of end-stage renal disease, Venous Needle Dislodgement (VND) is a rare, but potentially fatal situation in which the needle delivering a patient's blood back to the body after filtration by a dialysis machine becomes inadvertently disconnected from the patient. Hemotek Medical Inc. has developed the V Needle, a venous needle return that is designed to reduce patient risk from exsanguination-related injury or death. This clinical study will serve as a confirmatory study to gain FDA marketing clearance of the Hemotek V Needle system in the clinical setting. During this study, we will determine the ability of the V Needle to successfully deliver appropriate hemodialysis therapy per the facility's guidelines. It will also be used to determine if the V Needle triggers false blood alarms under normal operating conditions. This study will also be used to demonstrate the V Needle meets effective usability criteria. Rates of adverse events and ability to complete the hemodialysis session will be compared to the rates recorded using commercially available devices during the hemodialysis sessions prior to the use of the Hemotek V Needle.

This study is a prospective, multi-center, single-arm study with subjects acting as their own control designed to confirm the safety, performance, and usability of the V Needle, a new safety needle for use during in-clinic hemodialysis that is designed to automatically generate a partial occlusion of the internal fluid path and trigger the hemodialysis machine to alarm and shut off if a complete dislodgement of the venous needle from the arm inadvertently occurs.

The study is an open-label, non-randomized, single arm, multi-center trial with subject's serving as their own control. For the first three (3) control sessions, subjects will undergo usual hemodialysis sessions with a commercially available device. For the remaining six (6) sessions, subjects will be cannulated with a V Needle in place of a usual venous line AV fistula set.

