1.8 STUDY RATIONALE

In patients undergoing hemodialysis for the treatment of end-stage renal disease, Venous Needle Dislodgement (VND) is a rare, but potentially fatal situation in which the needle delivering a patient's blood back to the body after filtration by a dialysis machine becomes inadvertently disconnected from the patient. The use of the V Needle as a venous needle return is designed to significantly reduce patient risk from exsanguination-related injury or death. This clinical study will serve to confirm safety, performance, and usability of the device during appropriate hemodialysis therapy. During this study, the safety and performance of the V Needle during delivery of appropriate hemodialysis therapy will be tested. The study will also assess the number of false blood alarms observed under normal operating conditions and the V Needle's usability. V Needle rates of adverse events and ability to complete the hemodialysis session will be compared to the rates recorded using standard available needle sets during hemodialysis sessions prior to the use of the Hemotek V Needle.

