5.1 Overall Design

This study is a prospective, multi-center, single-arm study with subjects acting as their own control designed to confirm the safety, performance, and usability of the V Needle, a new safety needle for use during in-clinic hemodialysis that is designed to automatically generate a partial occlusion of the internal fluid path and trigger the hemodialysis machine to alarm and shut off if a complete dislodgement of the venous needle from the arm inadvertently occurs.

For the first three (3) control sessions, consenting subjects will undergo usual hemodialysis sessions with a commercially available device. For the remaining six (6) test sessions, subjects will be cannulated with a V Needle in place of a usual venous line AV fistula set.

The hemodialysis sessions will be conducted in the clinic. Subjects will be observed by a clinician for the duration of each session. Clinicians will monitor the session for any abnormal disruptions, therapy interruptions, and/or adverse events, including hemolysis, due to V Needle presence. All machine blood alarms, therapy interruptions, and/or partial or complete needle dislodgements will be recorded and immediately corrected. Clinicians will be responsible for identifying adverse events as they occur and will activate established facility emergency response plans if necessary. A clinician will perform cannulation.

Cannulation site and surrounding tissue will be examined by the nurse and assessed for any locally induced trauma before and after treatment.

A survey will be completed by the users to assess usability of the V Needle.

After the first five (5) patients will be enrolled, and data through the last visit of the fifth patient is available, this data will be submitted to the FDA while study enrollment and visits continue. No Hemotek Medical V Needle treatments will occur until after FDA has reviewed the data from the first 5 patients and allows the study to proceed. Data will also be submitted to the FDA after the tenth patient completes their last visit and data is available. After the tenth patient, study enrollment and visits can continue, but no Hemotek Medical V Needle treatments will occur on the final 5-10 patients until the FDA allows the study to proceed. After FDA has found the data for the first 10 patients acceptable, the rest of the study can continue until the end.

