7.3 Measures to Minimize Bias: Randomization and Blinding

The study is not randomized or blinded. Control sessions measuring the rates of adverse events and successful therapy sessions is included to provide a within-subject comparator to these rates for the V Needle. To minimize bias, subjects will be considered and asked to enroll in the study sequentially to the extent possible to ensure that no unconscious bias of patient selection occurs. The study will be conducted at multiple centers to ensure that outcomes are able to be generalized across different clinics.

At least two different clinicians will evaluate the device for each patient and for each needle for that patient (test and control) to minimize the bias associated with the same clinician evaluating all of the sessions for a given subject.

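### AE rates on the V Needle are to be compared with control sessions, but Section 10.3.2 gives one interval per needle and no difference or ratio

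*Combined protocol and SAP*

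**What the plan says.** **The intention.** Section 1.1 states: "Rates of adverse events and ability to complete the hemodialysis session will be compared to the rates recorded using commercially available devices". Section 3.1 repeats this. Section 1.8 says "V Needle rates of adverse events and ability to complete the hemodialysis session will be compared to the rates recorded", and Section 5.2 says "the rates of adverse events will be compared to rates measured using commercially available devices". Section 5.1 describes a "single-arm study with subjects acting as their own control". Section 7.3 names both AE rates and successful sessions and says that measuring them in control sessions "is included to provide a within-subject comparator to these rates for the V Needle".

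**The analysis.** Under Section 10.3.2 the AE rates "will be calculated as the number of events per number of treatments as well as tallied per subject". Then: "Adverse event rates will be summarized with 95% exact binomial confidence bounds for both the investigational and control groups". Events are also broken down by seriousness, severity, relatedness and anticipated status. An event arising between sessions is credited to the needle used last. No difference, ratio, test or paired method is named.

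**Elsewhere.** Section 10.4.1 presents summaries at session level and reserves within-subject analysis for the additional analysis of the primary performance measure. Between-needle methods are named for performance (Section 10.3.1) and for the surveys (Section 10.3.3), but not for AEs.

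**The concern.** The relative safety question is whether AEs are more frequent with the V Needle than with the usual needle. The control sessions are there partly to answer it, and Section 3.3.3 expects blood loss and air embolism to be no more frequent than in usual dialysis. Without an estimated contrast, a reader has two rates and two intervals to set side by side. Overlap of two 95% intervals is a blunt guide to whether the rates differ. It also does not show how large an excess the data leave open, which is the more useful figure in a study of about 18 subjects.

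**Working it through.** **Inputs.** 18 subjects, 108 V Needle and 54 control sessions (Section 10.3.1), so 6 and 3 per subject. The plan gives no AE rate and no precision or power for an AE comparison, so there is no AE figure to reproduce. Its 87 test sessions concern session success. They reproduce (exact power of the Farrington-Manning test 85.3–85.5% with 43 or 44 control sessions) but have no bearing here.

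**1. Two intervals against one contrast.** Assumed counts: 16 events in 108 sessions and 2 in 54, at most one per session, sessions independent.
- Rates: 16/108 = 14.8%; 2/54 = 3.7%; difference 11.1 points.
- Exact (Clopper-Pearson) 95% intervals: 8.7–22.9% and 0.5–12.7%. They overlap between 8.7 and 12.7%.
- Newcombe interval for the difference, from Wilson limits 9.3–22.7% and 1.0–12.5%: lower 11.1 − √((14.8−9.3)² + (12.5−3.7)²) = +0.7; upper 11.1 + √((22.7−14.8)² + (3.7−1.0)²) = +19.5. It excludes zero.

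**2. How often harm would be flagged.** Simulation with Poisson events, 20,000 runs per setting and a true doubling. The contrast conditions on total events n: the V Needle count is binomial(n, s), with s = 6/9 under no effect when every session has an equal capture window. One-sided level 2.5%.

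| Assumed control rate per session | Non-overlap | Conditional exact | Conditional mid-p |
|---|---|---|---|
| 0.02 | 0% | 0.5% | 3% |
| 0.05 | 2% | 9% | 15% |
| 0.10 | 11% | 24% | 32% |
| 0.20 | 40% | 52% | 58% |

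At 0.10 and a true tripling the figures are 54, 71 and 77%. With equal windows, the error under no effect was at most about 2.6%.

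**3. Does the gain come from pairing?** With full attendance every subject has the same s, so the conditional test reduces to pooled counts and subject identity drops out. Between-subject variation (gamma frailty, variance 1) at rate 0.10 moved the flagging rates only from 11.1 to 11.7%, 23.8 to 24.4% and 31.4 to 32.1%. The gain comes from having a contrast at all.

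**4. Is 6/9 the right share?** Not for events that accrue with time. At three sessions a week (Section 1.12) a gap is 7/3 = 2.33 days.
- Control: 3 × 2.33 = 7 days, ending at the first V Needle session.
- V Needle: 5 × 2.33 = 11.7 days, plus 7–10 days to the final contact (Sections 1.23 and 9.1.4) = 18.7–21.7 days.
- Null share: 18.7/25.7 = 0.73 to 21.7/28.7 = 0.76, against 6/9 = 0.67.

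In the worst case, with all events time-driven, no device effect and control rate 0.10, using 6/9 gives one-sided error of about 5–9% (exact) and 7–13% (mid-p) instead of 2.5%.

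The choice matters in the example. With the session share the rate ratio is (16/108)/(2/54) = 4.0 (95% mid-p 1.06 to 25.7). With days at risk the exposure ratio is 18.7/7 = 2.67 or 21.7/7 = 3.10 instead of 2. The ratio becomes 4.0 × 2/2.67 = 3.0 (0.79 to 19.3) or 4.0 × 2/3.10 = 2.6 (0.68 to 16.6), and both intervals include 1.

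**The case against.** The safety aim is descriptive. The only hypothesis is for performance, and Section 10.3.2 does set both needles' rates side by side with bounds, per-subject tallies and breakdowns. A comparison announced in a rationale section need not mean a test. That stands: what is missing is an estimate with its interval, not a powered test.

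A reader might infer that the plan will declare no harm when the intervals overlap. No section sets such a rule. The non-overlap figures show what informal reading could miss, not what the plan will decide.

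A reader might also infer that the main loss is the unused own-control structure. Section 10.3.2 does lack a within-subject AE comparison, but step 3 shows that pairing itself adds almost nothing at full attendance. Conditioning on subject matters when attendance or days at risk differ between subjects.

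Nor does the main safety conclusion depend on this contrast. The primary safety measure is the SADE rate, and device effects are defined in Section 9.2.1 for the investigational device, so they have no control counterpart. Board review of serious events, the stopping rule in Section 5.3 and the staged FDA reviews also stand apart from it.

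Finally, control sessions always come first, so any ratio mixes needle with period. That is true, and it applies equally to the side-by-side rates.

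**Conclusion.** The gap is real but limited. The protocol announces an AE comparison, and the safety analysis stops at one interval per needle. At an assumed control rate of 0.10 per session and a true doubling, a mid-p contrast would flag harm about 32% of the time, against 11% by non-overlap. At 0.02 the figures are 3% and 0%, so for SAEs the contrast would be close to uninformative. All these rates are assumptions, and the simulated figures require equal capture windows per session. Primary performance inference and the SADE rate are unaffected. This is a cheap improvement of minor to moderate severity.

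**What to change.** Add a paragraph to Section 10.3.2, labelled descriptive:
- For AEs and SAEs, report the V Needle/control rate ratio (or difference) with a 95% interval, conditional on subject, beside the per-needle rates.
- Match exposure to capture. Either count only events from the start of a session to the start of the next dialysis, with the same window cap for both needles, including after the last V Needle session; or use each subject's days at risk on each needle as the offset. Name one as the main analysis and report the other as a sensitivity analysis. Do not use a fixed 6/9 share with the present capture windows. Days at risk would also reflect any wait between control and V Needle sessions during FDA review (Section 5.1).
- State that the fixed control-then-test order confounds needle with period.
- Leave SADEs and other device effects out of the contrast.

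The cost is one paragraph and one table, with no new visits or subjects. The windows and days at risk follow from session dates and AE onset; a cut at the start of the next dialysis also needs onset time, which Section 9.2.13 already collects. The downside is wide intervals, with almost no information on rare events.
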